6.1.2 Co-primary, Key-Secondary and Secondary Efficacy Variables

The co-primary efficacy variable, the key-secondary efficacy variables and the secondary efficacy variables will be determined for MP only.

- Co-primary efficacy variable is the Investigator's Global Impression of Change Scales (GICS) for upper limb at Day 29 (Week 4) of MP. The definition of this variable was changed compared to the CSP (for details see section 8).

The GICS are subjective global outcomes to assess independently the investigator's, child's/adolescent's, and parent's or caregiver's (if applicable) impression of change due to treatment. Caregiver(s) may substitute parent(s) for the assessment of GICS, if they are main social contacts of subjects, e.g. in a special-care home.

The question of the GICS for the investigator is: 'Based on your clinical experience, what is your overall impression of change of the subject's upper limb spasticity due to treatment, compared to the condition before the last injection? Please check the one option that best fits your overall impression of change.'

The response option for all GICS versions is a common 7-point Likert scale that ranges from -3 = very much worse to +3 = very much improved:

- +3 Very much improved
- +2 Much improved
- +1 Minimally improved
- 0 No change
- 1 Minimally worse
- 2 Much worse
- 3 Very much worse

Key-secondary efficacy variables are:

- Change from baseline in AS score of the **other treated main clinical target pattern** (i.e. of elbow flexors or wrist flexors, if treated) at Day 29 (Week 4) of MP. This analysis will be performed for the main clinical target pattern not analyzed as primary efficacy variable, in case two target patterns would qualify as main clinical target pattern.
- Change from baseline in AS score of treated clinical target pattern clenched fist (in subjects treated in combination with flexed wrist) at Day 29 (Week 4) of MP.

Secondary efficacy variables are:

- Change from baseline in AS score for each treated clinical pattern (e.g., flexed elbow, flexed wrist, clenched fist, pronated forearm and thumb in palm) of the UL at all other post baseline visits of MP (V3, V4, and V5). The definition of this variable was made more precise compared to the CSP (for details see section 8).
- Change from baseline in scores of pain intensity (from subjects) and pain frequency (from parent/caregiver) assessed with ‘Questionnaire on Pain caused by Spasticity (QPS)’ to all post baseline visits of MP (V3, V4, and V5). In the definition of this variable the visit numbers were added.

The QPS is a patient-reported outcome for children and adolescents (2-17 years) with CP on spasticity-related pain. For this study, in addition to the UL versions that will be used for all subjects/parents/caregivers, the LL versions will also be used for subjects with treatment combinations including UL and LL treatment. While pain intensity is reported by the children/adolescents, pain frequency (based on observed pain behaviors) will be documented by the parent(s)/caregiver(s). In addition, parent(s)/caregiver(s) report on pain location and observed pain behaviors. Thus, the information provided by the children/adolescents complements the one of the parents/caregivers. Pain intensity and frequency of the QPS are assessed for general pain and for four different activity situations. The situations are described in different questions for rest, normal day activities, physical exercise and for an individually defined ‘very hard thing to do’. First it is always asked if spasticity-related pain for each activity situation occurred (Yes/No) and then how severe the experienced spasticity was (6-point rating scale) or how frequent pain behavior was observed (5-point rating scale).

From the self-administered version and from the interviewer-administered version of the QPS the QPS child/adolescent score will be calculated as sum of the activity related pain items No. 5, 7, 9, and 12 divided by 4. In case one or more of the 4 items are missing the corresponding QPS score will not be calculated. The item No. 3 of the self-administered version and the interviewer-administered version will be not included into this score, but will be assessed separately as child/adolescent general pain intensity item.

From the parent/caregiver version the QPS parent/caregiver score will be calculated as sum of the items No. 9b, 10b, 11b, and 13b divided by 4. In case one or more of the 4 items are missing the corresponding QPS score will not be calculated. The item No. 8 of the parent/caregiver version will be not included into this score, but will be assessed separately as parent/caregiver general pain frequency item.

The QPS scores will be calculated separately for upper limb spasticity-related pain and for lower limb spasticity-related pain. Only the QPS versions applicable for the chosen treatment combination (A-E) will be utilized (i.e. UL or UL and LL). The different final versions of the questionnaire are displayed in Appendix 16.6 of the CSP.

- Child's/Adolescent's (if applicable) and Parent's/Caregiver's GICS at Day 29 (Week 4) of MP for upper limb. The definition of this variable was changed compared to the CSP (for details see section 8).

The question of the GICS for the Child/Adolescent is: 'What is your overall impression of change of your upper limb tightness due to treatment, compared to the condition before the last injection? Please check the one option that best fits your overall impression of change.'

The question of the GICS for the Parent/Caregiver is: 'What is your overall impression of change of child's/adolescent's upper limb spasticity (tightness) due to treatment, compared to the condition before the last injection? Please check the one option that best fits your overall impression of change.'

The same 7-point Likert scale as for the investigator will be used that ranges from -3 = very much worse to +3 = very much improved:

[REDACTED]

[REDACTED]

[REDACTED]

[REDACTED]

[REDACTED]

[REDACTED]

[REDACTED]

[REDACTED]

[REDACTED]

[REDACTED]

[REDACTED]

[REDACTED]

[REDACTED]

[REDACTED]

[REDACTED]

[REDACTED]

[REDACTED]

6.2 Pharmacodynamic Variables

Not applicable.

6.3 Pharmacokinetic Variables

Not applicable.

6.4 Pharmacogenetic Variables

Not applicable.

6.5 Safety Variables

6.5.1 Primary Safety Variable

Not applicable.

6.5.2 Secondary Safety Variables

Secondary safety variables of the MP comprise:

- Occurrence treatment emergent adverse events (TEAEs)
- Occurrence of treatment emergent adverse events of special interest (TEAESIs)
- Occurrence of serious TEAEs
- Occurrence of TEAEs related to treatment as assessed by the investigator
- Occurrence of TEAEs by worst intensity
- Occurrence of TEAEs by worst causal relationship
- Occurrence of TEAEs by worst outcome
- Occurrence of TEAEs leading to discontinuation

Secondary safety variables of the OLEX Period comprise:

- Occurrence of treatment emergent adverse events (TEAEs) overall and per treatment cycle.
- Occurrence of treatment emergent adverse events of special interest (TEAESIs) overall and per treatment cycle.
- Occurrence of serious TEAEs overall and per treatment cycle.
- Occurrence of TEAEs related to treatment as assessed by the investigator overall and per treatment cycle.
- Occurrence of TEAEs by worst intensity overall and per treatment cycle.
- Occurrence of TEAEs by worst causal relationship overall and per treatment cycle.
- Occurrence of TEAEs by worst outcome overall and per treatment cycle. The definition of this variable was changed compared to the CSP (for details see section 8).
- Occurrence of TEAEs leading to discontinuation overall and per treatment cycle.

6.5.3 Other Safety Variables

Other safety variables of the MP comprise:

- Investigator's Global Assessment of Tolerability at the Final Visit of MP V5 (In the definition of this variable the visit number was added.)
- Vital signs (blood pressure, heart rate) at all visits of MP
- Body Mass Index (BMI), weight and height at Screening V1, Baseline Injection Visit V2, at the Final Visit of MP V5
- Clinical chemistry, differential count and hematology at Screening V1
- Occurrence of antibodies against BoNT-A in subjects ≥ 21 kg BW at Screening V1
- Number of subjects with suicidal ideation, suicidal behavior, and self-injurious behavior without suicidal intent based on the Columbia-Suicide Severity Rating Scale (C-SSRS) This scale is used to assess suicidality prospectively in this clinical study at baseline and all post-baseline visits of the MP.

Other safety variables of the OLEX comprise:

- Investigator's Global Assessment of Tolerability at Day 99 (Week 14) of all OLEX cycles, i.e. at End of Cycle Visit (V9, V13) and at End of Study Visit (V17). In the definition of this variable the visit numbers were added.
- Vital signs (blood pressure, heart rate) at all visits of OLEX period (V6, V7, ..., V17). In the definition of this variable the visit numbers were added.
- BMI, weight and height at all Injection Visits of OLEX (V6, V10 and V14) and at the End of Study Visit (V17). If V5 and V6 will be performed at the same day, BMI, weight and height can be transferred from V5 to V6.
- Clinical chemistry, differential count and hematology at the Injection Visit V6 of OLEX and the End of Study Visit (V17).
- Occurrence of antibodies against BoNT-A in subjects ≥ 21 kg BW at the End of Study Visit (V17). In the definition of this variable the visit numbers were added.
- Number of subjects with suicidal ideation, suicidal behavior, and self-injurious behavior without suicidal intent based on the Columbia-Suicide Severity Rating Scale (C-SSRS) This scale is used to assess suicidality prospectively at all OLEX visits.

6.6 Other Variables

Other variables of interest are:

- Subject dispositions (including number of subjects enrolled, number of discontinuations and reason for discontinuations)
- Demographic data
- Other baseline characteristics such as:
 - Medical history and concomitant diseases
 - Previous and concomitant therapies, including medication and non-drug treatment
 - CP history (including main cause for cerebral palsy, affected limbs (UL unilateral left, UL unilateral right, ULs bilateral, LL unilateral left, LL unilateral right, LLs bilateral), duration since first diagnosis of spasticity, and duration since the first diagnosis of cerebral palsy)
 - Primary clinical pattern
 - GMFCS-E&R level:
1 = Level I: Walks without Limitations

- 2 = Level II: Walks with Limitations
- 3 = Level III: Walks Using a Hand-Held Mobility Device
- 4 = Level IV: Self-Mobility with Limitations; May Use Powered Mobile
- 5 = Level V: Transported in a Manual Wheelchair

- Planned treatment of spasticity: treatment combinations A, B, C, D, and E, limbs planned to be treated (lower limb right, lower limb left, upper limb right, and upper limb left), and primary body side for analyses, if bilateral: This variable was added in the SAP (for details see section 8).
- BoNT-A pre-treatment status
- Use of local anesthesia/analgo-sedation for injection treatments:
 - Inhalative sedatives (e.g. nitrous oxide, sevoflurane)
 - Oral sedatives (e.g. benzodiazepines, antihistamines)
 - Rectal sedatives (e.g. benzodiazepines)
 - Parenteral sedatives (e.g. benzodiazepines, propofol)
 - Topical/Local anaesthetics (e.g. lidocaine/prilocaine cream)
 - Oral analgesics (e.g. paracetamol, opioids)
 - Rectal analgesics
 - Parenteral opioid analgesics
 - Parenteral non opioid analgesics
 - Topical cooling (e.g. cooling spray)
 - Other
- Monitoring during sedation (yes/no): This variable was added in the SAP (for details see section 8).
- Injection guidance technique (ultrasound, electromyography (EMG)/ electrical stimulation (e-stim), e-stim, EMG): This variable was added in the SAP (for details see section 8).
- Treatment compliance: This variable was added in the SAP (for details see section 8).
- Extent of exposure (injected volume, injected units, number of injected sites per body side, per clinical pattern, and per muscle and in total, and frequency of treated limbs

and number (%) of subjects with unilateral and with bilateral treatment by upper and lower limbs): This variable was added in the SAP (for details see section 8).

- Length of injection cycles and the total observation period in weeks over the entire study. This variable was added in the SAP (for details see section 8).


For efficacy variables the last measurement before start of treatment is defined as baseline value.

Testing of the primary, co-primary and key-secondary efficacy variables of the MP will be performed in a 4-step approach using a hierarchical test procedure as described below:

1. Step: Primary and co-primary efficacy variables for high dose vs. low dose.
2. Step: First key-secondary efficacy variable and co-primary efficacy on subpopulation variables for high dose vs. low dose.
3. Step: Second key-secondary efficacy variable for high dose vs. low dose.
4. Step: Primary and co-primary efficacy variables for mid dose vs. low dose.

Due to the hierarchical testing strategy of (co-)primary and key-secondary efficacy variables and the two dose group comparisons (high versus low and mid versus low), this four step hierarchical testing procedure ensures the overall type I level of 5% for the confirmatory tests. If one of four hierarchical tests does not yield a statistically significant result, the consecutive test(s) will still be performed but will be considered to be only descriptive.

The estimand of interest of this study is the treatment effect measured by the primary and co-primary efficacy variables in all subjects of FAS of the MP regardless of adherence to randomization list.

7.1.1 Primary Efficacy Variable

The primary efficacy variable is the change from baseline in AS in the primary clinical target pattern, i.e. elbow flexors or wrist flexors, at Day 29 (Week 4) of MP. A mixed model repeated measurement analysis (two-sided, significance level $\alpha=0.05$) with comparison of least square means will be used for the confirmatory analysis to detect differences between the high and low dose treatment groups. The following working hypotheses will be tested by use of a two sample t-test:

$$H_0: \mu_{NT201_high} - \mu_{NT201_low} = 0 \quad \text{vs.} \quad H_1: \mu_{NT201_high} - \mu_{NT201_low} \neq 0$$

with μ denoting the mean change from baseline. Stronger negative differences between least square mean estimates as defined by the working hypotheses thereby indicate better results (stronger reduction of AS from baseline to V3) in the high dose group compared to the low dose group.

Estimates for least square means will be derived from the mixed model repeated measures where the dependent variable in the model is defined as the change from baseline in the AS. The independent variables are defined as treatment group (high dose, low dose), pooled sites, BoNT-A pre-treatment status (pre-treated, treatment naïve) as fixed factors, visit*treatment as interaction term, and visit as repeated factor. Covariates are the AS score of the primary clinical target pattern at baseline (Day 1 of MP) and the GMFCS-E&R level at screening. The following SAS code will be used:

```
proc mixed data = dataset;  
  class treatment site btx subject visit;  
  model AS_change = treatment site btx AS_baseline GMFCS  
    visit visit*treatment / solution ddfm=kr;  
  repeated visit / subject= subject TYPE=un;  
  lsmeans visit*treatment / diff cl pdiff;  
run;
```

Sites will be pooled for the statistical analysis based on geographic criteria. For definition of pooling rules please refer to section 7.7.6.

Confirmatory testing will be performed on the FAS of MP with accounting for missing values using the mixed model repeated measures (MMRM) approach.

In order to investigate the impact of missing values and different approaches for imputation, further sensitivity analyses will be performed on the PPS as well as on the FAS of the MP using the LOCF principle and without missing replacement (observed case analysis). For this purpose the statistical model as described above but without visit*treatment as interaction and without visit as repeated factor will be applied for LOCF analysis and for observed case analysis. Since there is no assessment of AS between baseline and V3, the baseline observation will be carried forward to Week 4 equals the LOCF analysis. Therefore the LOCF method is equivalent to the baseline observation carried forward (BOCF) method in this special case. The following SAS code will be used:

```
proc mixed data = dataset;  
  class treatment site btx;  
  model AS_change_wk4 = treatment site btx AS_baseline GMFCS / solution  
    ddfm=kr;  
  lsmeans treatment / pdiff CL alpha=0.05;  
run;
```

Further, a non-parametric Wilcoxon rank-sum test will be performed as sensitivity analysis of the primary efficacy variable to investigate the impact of potential deviations from the assumption of normal distribution (for FAS of the MP and PPS subset, using LOCF). The following working hypotheses will be tested:

H₀: Prob. distributions for high dose group and low dose group are identical

vs.

H₁: Prob. distribution for high dose group shifted to right or left of distribution for low dose group.

The Wilcoxon rank-sum test will be performed by use of the following SAS code:

```
proc npar1way data=dataset wilcoxon;  
  class treatment;  
  var AS_change_wk4;  
  exact;
```

run;

Furthermore, descriptive summary statistics, shift tables and frequency tables of changes will be given for the primary efficacy variable.

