### **8.2.1 Methods of assigning subjects to treatment groups**

The study is planned as an international multi-center study. At the Baseline Injection Visit (Day 1) of the double-blind MP, subjects will be assigned to one of three dose groups of NT 201 (high, mid, and low) according to a 2 : 1 : 1 randomization scheme.

Randomization will be balanced in blocks of appropriate size. The distribution of the IP to the investigational sites and the randomization will be controlled by IV/WRS to ensure a number of enrolled subjects approximately according to the randomization ratio of 2 : 1 : 1 in the three treatment groups. Subjects discontinued from the study will not be replaced.

In this study, two main clinical target patterns have been defined, i.e. *flexed elbow* with an assessment of the AS score for elbow flexors and *flexed wrist* with an assessment of the AS score for wrist flexors. Randomization will be stratified by primary clinical pattern (elbow flexors/flexed wrist) in a 1:1 ratio within each dose group.

In practice, a subject may have up to two main clinical target patterns qualifying for primary efficacy analysis based (a) on the clinical need for IP injection and (b) on the presence of an AS score  $\geq 2$  in elbow or wrist flexors. Since no clinical algorithm is existent to decide which of both main clinical target patterns to take for primary efficacy analysis in such a situation, an IV/WRS will be used to achieve an overall equal distribution of primary clinical target patterns flexed elbow and flexed wrist in this study. The selection will be performed by the IV/WRS before randomization to treatment groups (i.e. to one of three dose groups of NT 201 in MP). In case only one main clinical target pattern qualifies for primary efficacy analysis, this pattern will be selected by the IV/WRS. If both main clinical target patterns would qualify for primary efficacy analysis,

the selection has to be in a way that after randomization the distribution of primary clinical target patterns is balanced as much as possible in both treatment groups, or at random, if this is not possible.

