4 DETERMINATION OF SAMPLE SIZE

The sample size estimation for the primary efficacy variable 'change from baseline in AS in the primary clinical target pattern, i.e. elbow flexors or wrist flexors, at Day 29 (Week 4)' was based on data of a study with BoNT-A in the treatment of post-stroke UL spasticity in adults [Childers 2004 (1)]. In this trial a modification of the original 5-point AS to a 9-point scale by adding 4 half point increments was used. Since this modified Ashworth Scale (MAS) is very similar to the original Ashworth Scale (AS) used in the present study, it appeared to be justified to base the sample size calculation on the MAS results of the study by Childers et al.. In this study, a mean change from baseline in MAS scores at the elbow of -1.01 in the 180 U BoNT-A dose group and of -0.7 in the 90 U dose group were observed. It was assumed that the changes from baseline in AS for flexed elbow will be comparable to the one for flexed

wrist. The 180 U dose lies between the 200 U and the 150 U (for subjects ≥ 25 kg) doses planned for the high and mid dose group in this study. Since published trial data for the exact doses planned in this trial did not exist, and doses of BoNT-A applied in spasticity show complex non-linear correlations to AS scores [Yablon 2011 (2)], it appeared to be justified to use the same assumptions for both dose groups.

Comparable Placebo (PBO)-controlled studies showed a low drop-out rate of 3% at the time of assessment of the primary efficacy variable. Therefore, a similarly small number of missing data for the primary efficacy endpoint was expected for this study. Consideration of assumptions above with a 3% rate of missing values and using last observation carried forward (LOCF) as originally planned in the CSP led to the group means $\mu_{NT201_high} = -0.98$, $\mu_{NT201_mid} = -0.98$ and $\mu_{NT201_low} = -0.68$.

The assumption for a pooled common standard deviation (SD) was $\sigma = 0.6$.

An estimated total number of 258 (with randomization ratio of 2:1) subjects will provide 96.5% power to show a statistically significant difference between the NT 201 high dose group (172 subjects) and the NT 201 low dose group (86 subjects) at an alpha level of 0.05 (two-sided t-test, Statistical Analysis System software[®]).

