7.1.2 Co-Primary, Key-Secondary and Secondary Efficacy Variables

Co-primary efficacy variable:

1. Step: Both, the primary efficacy variable and the co-primary efficacy variable have to show statistically significant treatment differences in order to prove superiority of high dose vs. low dose treatment. No α -adjustment for multiplicity is necessary.

The co-primary efficacy variable is the Investigator's Global Impression of Change Scales (GICS) for upper limb at Day 29 (Week 4) of MP. As for the primary efficacy variable, an analysis of covariance (ANCOVA) approach (2-sided, significance level $\alpha=0.05$) with comparison of least square means will be used for the confirmatory analysis of the co-primary efficacy variable. The dependent variable is defined as the 'Investigator's GICS at Day 29 (Week 4) for upper limb of MP'. The independent variables are defined as treatment group (high dose, low dose), pooled sites, BoNT-A pre-treatment status (pre-treated, treatment naïve) as fixed factors and the covariates are the maximum AS score of the two possible primary target clinical patterns flexed elbow or flexed wrist at baseline (Day 1 of MP) and the GMFCS-E&R level at Screening Visit. The following SAS code will be used:

```
proc mixed data = dataset;  
  class treatment site btx;  
  model I_GICS_wk4 = treatment site btx max_AS_baseline GMFCS / solution;  
  lsmeans treatment / pdiff CL alpha=0.05;  
run;
```

Positive values for differences between least square mean estimates as defined by the working hypotheses (see primary efficacy variable) thereby indicate better results (higher GICS values at Day 29, Week 4) in the high dose group as compared to the low dose group. Confirmatory testing will be performed on the FAS of MP with replacement of missing data, setting all missing values of the co-primary efficacy variable to "0" (no change).

Further sensitivity analyses will be performed on the PPS as well as on the FAS of the MP and the PPS without missing replacement (observed case analysis).

Further, a non-parametric Wilcoxon rank-sum test will be performed as sensitivity analysis to investigate the impact of potential deviations from the assumption of normal distribution (for FAS and PPS subset, imputing missing data by "0", i.e. no change). The same SAS code as for the primary efficacy variable will be used with primary efficacy variable replaced by co-primary efficacy variable.

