Furthermore, frequency tables and descriptive summary will be performed for the co-primary efficacy variable.

Key-secondary efficacy variables and co-primary efficacy variable restricted to subpopulation:

2. Step: If the confirmatory tests of the primary efficacy variables and the co-primary efficacy variable both show significant results, then the hierarchical testing approach will be continued in a second step. In this second step the following two variables will be tested for high dose group versus low dose group:

- First key secondary efficacy variable: Change from baseline in AS score of the **other treated main clinical target pattern** (i.e. of elbow flexors or wrist flexors, if treated) at Day 29 (Week 4) of MP
- Co-primary efficacy variable: Investigator's Global Impression of Change Scales (GICS) for upper limb at Day 29 (Week 4) for the following subpopulation:

This analysis will be done for the subpopulation defined by this key-secondary endpoint, that means only subjects having two main clinical target patterns will be included into the analysis. All subjects with only one main target pattern will be excluded from the analysis. The analysis models will be identical to the analyses described above for the 1st step using the the key-secondary variable instead of the primary variable and the co-primary variable restricted to the subpopulation instead of the co-primary variable of the unrestricted population.

Both, the first key-secondary efficacy variable and the co-primary efficacy variable for the subpopulation have to show statistically significant treatment differences in order to prove superiority of high dose vs. low dose treatment in this subpopulation.

3. Step: Only if the confirmatory analysis of step 2 yields a statistically significant result, in a third step, a confirmatory analysis of the second key-secondary efficacy variable 'change from baseline in AS score of clinical target pattern clenched fist (in subjects treated in combination with flexed wrist), at Day 29 (Week 4) of MP will be done. This variable has been chosen, since it is anticipated that the vast majority of subjects will have a combined clinical presentation of clinical patterns clenched fist and flexed wrist. Subjects with either treatment alone (i.e. clenched fist or flexed wrist) with other clinical target patterns will be evaluated separately in a descriptive manner as other efficacy variables (see also section 6.1.3 and 7.1.3).

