4. Step: Only if the confirmatory analysis of step 3 yields a statistically significant result, in a fourth step, using a hierarchical testing approach, the mid dose treatment will be compared to low dose treatment for the primary efficacy variables and the co-primary efficacy variable. The analysis models will be identical to the analyses described above for the 1st step replacing high dose group with mid dose group. Both, the primary efficacy variable and the co-primary efficacy variable have to show statistically significant treatment differences in order to prove superiority of mid dose vs. low dose treatment.

For the confirmatory analyses a two-sided significance level of $\alpha=0.05$ will be applied and analysis models as described for the (co)-primary efficacy variables will be applied. The

analysis of the primary efficacy variable and of both key-secondary efficacy variables will be performed on the FAS of the MP with an MMRM approach. For the co-primary efficacy variable and the co-primary variable restricted to the subpopulation, missing data will be imputed by "0", i.e. no change.

All other test procedures will be explorative. Sensitivity analyses will be performed on the PPS of MP using the MMRM approach, as well as on the FAS and the PPS of MP using a mixed model approach without repeated measures first with the LOCF principle and second without replacement of missing values (i.e., observed case analysis). As the GICS is measured at Control Visit V3 only it is not possible to apply a model based analysis like mixed model repeated measurement.

Secondary efficacy variables:

All secondary variables will be analyzed on the FAS of the MP and the PPS. All tests will be descriptive and interpreted in an explorative manner. Treatment comparisons will be tested for comparison of the high versus low dose treatment group and the mid versus low dose treatment group, respectively.

Ashworth scale of the UL

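### Randomisation is stratified by primary clinical pattern (elbow or wrist), but the confirmatory models leave that factor out without a reason; if the two patterns respond differently, the AS tests are conservative and lose some power.

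*SAP*

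**What the plan says.** Protocol section 8.2.1 states: "Randomization will be stratified by primary clinical pattern (elbow flexors/flexed wrist) in a 1:1 ratio within each dose group". The study population section (Protocol section 7) gives the resulting split: 86 elbow and 86 wrist in the high dose group, and 43 and 43 in each of the mid and low dose groups.

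The confirmatory AS model in SAP section 7.1.1 is described as "The independent variables are defined as treatment group (high dose, low dose), pooled sites, BoNT-A pre-treatment status" as fixed factors, with a visit-by-treatment interaction, visit as repeated factor, and baseline AS and GMFCS level as covariates. The SAS code agrees with the text: "model AS_change = treatment site btx AS_baseline GMFCS", followed by the visit terms. The LOCF and observed-case versions use "model AS_change_wk4 = treatment site btx AS_baseline GMFCS / solution". The co-primary GICS model in section 7.1.2 is "model I_GICS_wk4 = treatment site btx max_AS_baseline GMFCS / solution". None contains pattern.

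The later steps inherit these models. For step 2: "The analysis models will be identical to the analyses described above for the 1st step using" the key-secondary variable and the restricted GICS. For step 4: "The analysis models will be identical to the analyses described above for the 1st step replacing high dose group with mid dose group". Protocol section 12.4.1.1 also specifies the models without pattern.

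The only statement bearing on the omission is in the sample-size section (SAP section 4): "It was assumed that the changes from baseline in AS for flexed elbow will be comparable to the one for flexed" wrist. It is not offered as a reason for the model.

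**The concern.** When arms are balanced on a factor that predicts outcome, the treatment contrast no longer carries that factor's variance. A model that omits the factor still counts this variance as residual noise. The estimated standard error is then larger than the true sampling error, confidence intervals are too wide, and the test rejects less often than its nominal level.

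Pattern is a plausible predictor here. The two patterns involve different muscles, and Protocol section 8.1.1.2 gives them different fixed doses (4 U/kg for flexed elbow and 2 U/kg for flexed wrist in the high dose group). Equal mean change is therefore not assured, and the planning data were elbow data only.

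What is at stake is efficiency, not validity. The cost falls mainly on mid vs low, the last of the four gated steps, which has the lowest planned joint power: 0.903 × 0.967 = 87.3%.

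**Working it through.** **Inputs.** From SAP section 4: group means -0.98, -0.98 and -0.68, so the treatment difference is 0.30 for both comparisons; SD 0.6; two-sided alpha 0.05; 172 vs 86 and 86 vs 86 subjects. From Protocol section 7: patterns split 50/50 within each arm. Assumed, because no document gives it: the gap g between elbow and wrist in mean AS change, taken as 0.2, 0.3 and 0.5. The main reading treats 0.6 as the within-pattern SD, since the planning data were for the elbow.

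**Step 1: reproduce the stated power.** Noncentrality = 0.30 / (0.6 × sqrt(1/n1 + 1/n2)).

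- High vs low: 0.30 / 0.07924 = 3.786. The noncentral t gives 96.5%, as stated.
- Mid vs low: 0.30 / 0.09150 = 3.279. The noncentral t gives 90.3%, as stated.

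**Step 2: overstatement of the standard error.** A 50/50 mix of two patterns g apart adds g²/4 to the residual variance. The true sampling variance of the treatment effect still uses 0.36. The ratio of estimated to true standard error is r = sqrt(1 + g²/(4 × 0.36)) = sqrt(1 + g²/1.44):

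- g = 0.2: sqrt(1.0278) = 1.014
- g = 0.3: sqrt(1.0625) = 1.031
- g = 0.5: sqrt(1.1736) = 1.083

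**Step 3: type I error and power with pattern omitted.** The effective critical value becomes t_crit × r. Type I error is P(|t| > t_crit × r); power is the same tail under the noncentral t.

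| g | SE overstated by | Type I error | Loss from 96.5%, high vs low | Loss from 90.3%, mid vs low |
|---|---|---|---|---|
| 0 | 0% | 5.0% | 0 | 0 |
| 0.2 | 1.4% | 4.7% | 0.2 points | 0.5 points |
| 0.3 | 3.1% | 4.3% | 0.5 points | 1.1 points |
| 0.5 | 8.3% | 3.4% | 1.5 points | 3.1 points |

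**Step 4: loss expressed as sample size, mid vs low.** The equivalent fraction is ((3.279 - 1.96 × (r - 1)) / 3.279)², which gives 0.984, 0.964 and 0.903. The omission is worth 1.6%, 3.6% and 9.7% of the sample.

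**Step 5: the other reading of the SD.** If 0.6 already contains the between-pattern variance, the within-pattern SD is sqrt(0.36 - g²/4) = 0.592, 0.581 and 0.545. Planned power is then not lost. Adding the factor would gain 0.2, 0.4 and 0.9 points (high vs low) and 0.5, 1.0 and 2.5 points (mid vs low).

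**Step 6: simulation check.** With 200,000 trials per cell, comparing treatment alone with treatment plus pattern at g = 0.2, 0.3 and 0.5:

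- Mid vs low power: 90.0%, 89.3%, 87.1% omitted; 90.4%, 90.3%, 90.3% included.
- High vs low power: 96.3%, 95.9%, 95.0% omitted; 96.5%, 96.4%, 96.4% included.
- Type I error at g = 0.5: 3.4% omitted; 5.0% included.

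**The case against.** The strongest reply is that the documents assume comparable elbow and wrist changes, and under that assumption the cost is zero. Every non-zero figure rests on a gap chosen for illustration, and 0.5 exceeds the planned treatment difference of 0.30. That is true, which is why a range starting at zero is shown. But the assumption was made to size the trial; the confirmatory test need not depend on it.

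Second, the figures lean towards upper bounds. Baseline AS may absorb part of a gap, the 50/50 split maximises the added variance, and the check is a single-visit model standing in for the Week 4 MMRM contrast. This stands and limits the size, not the direction.

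Third, the wording on the SD is ambiguous, and on the second reading planned power is met anyway. This also stands, but the unadjusted test is still conservative and less powerful than the adjusted one whenever the gap is not zero.

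Fourth, SAP section 8 lists changes from the protocol, and the protocol model already lacked pattern, so silence there is unsurprising. Fair; but no reason appears in the protocol either.

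Fifth, a main effect for pattern deals only with a gap in mean change, not with different treatment effects by pattern. Correct. With effects of 0.15 and 0.45 and no other gap, power changes by only about 0.2 to 0.3 points between the two models.

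Finally, per-pattern MMRMs are planned. They are exploratory and leave the confirmatory models as they are; primary pattern is also absent from the AS subgroup list in SAP section 7.7.5.

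**Conclusion.** The concern holds. The trial's stratification factor is missing from every confirmatory model, with no reason given. Type I error is not inflated. For gaps of 0.2 to 0.5 AS points, and with 0.6 as the within-pattern SD, the AS test runs at 4.7% to 3.4% and gives up 0.2 to 1.5 power points (high vs low) or 0.5 to 3.1 points (mid vs low). These sizes assume an even split of patterns and no absorption by baseline AS; with no gap the cost is nil.

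The case is clearest for the AS tests at steps 1 and 4, where balance on pattern is built into the randomisation. At step 2 the subpopulation is not itself a stratum, so the benefit is ordinary precision. It is weak for GICS, because where both patterns qualify the label is chosen by the IV/WRS, and for step 3, where every subject is scored on clenched fist. The change should be made, but the trial's validity does not depend on it.

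**What to change.** Before unblinding:

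- Add primary clinical target pattern as a class factor to the AS MMRM and to its LOCF and observed-case versions at steps 1 and 4.
- At step 2, add the pattern being analysed. This is the same two-level split, because every subject there has both patterns.
- For consistency, add the factor to the GICS ANCOVA.
- Use the pattern as selected by the IV/WRS. SAP section 6.1.1 sets the derived pattern to missing when the primary pattern was mistakenly left untreated, and subjects with that value missing would drop out of the GICS model, although SAP section 8 keeps those with an upper-limb GICS in the FAS.
- If the factor is to stay out, say why in the SAP.

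A pattern-by-visit term in the MMRM, and a van Elteren test alongside the Wilcoxon test, are optional.

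The cost is one class variable in the SAS code, one sentence in the SAP and one degree of freedom. No new data are needed.
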